9.2.2. Outcome measures

The following outcome measures are assessed post-discharge, and will be measured during the variable post-index period starting on the treatment index date for the apixaban and warfarin cohorts.

Treatment patterns

- Persistent days (mean, SD, median, IQR, min, max) will be reported for patients until they discontinue, switch or end of follow-up based on definitions below
- Patients discontinuing outpatient treatment of apixaban or warfarin, respectively (NDC codes from LRx; n, %)

Note: Discontinuation will be defined as the occurrence of a ≥ 30 day gap from the run-out of days' supply of the treatment (post-discharge) index prescription (i.e. apixaban or warfarin) to the date of the next claim for the respective therapy or with no other claims for the respective therapy. The date of the discontinuation will be defined as the last day of the days' supply of the last filled prescription.

- Time (in days) from treatment index date to discontinuation date (mean, SD, median, IQR, min, max)

Note: Kaplan-Meier (KM) curves will be generated to measure median time (and 95 % CI) to discontinuation.

- Patients switching to an OAC other than apixaban or warfarin, respectively (switched) (NDC codes from LRx; n, %)

Note: Patients will be considered to have switched if they filled a prescription for OAC other than apixaban or warfarin, respectively (identified through NDC codes in LRx) or for PAC within 30 days before or after the run out date of index treatment. The date of the switch will be defined as date of the prescription of such a therapy (OAC or PAC).

- Time (in days) from treatment index date to switch date, defined as the date of the first claim for the new OAC or PAC (mean, SD, median, IQR, min, max)

Note: KM curves will be generated to measure median time (and 95 % CI) to switching

Clinical Outcomes

The following clinical outcomes will be assessed during the time patients are persistent with their respective index apixaban or warfarin treatment (treatment index):

- Patients with ≥ 1 hospitalization for recurrent VTE (ICD-10 codes in CDM; n, %)
- Incidence rate (IR) of recurrent VTE (per 100 patient years)
 - The date of the first observed event will be flagged. The numerator for IR will be the number of patients with the event of interest and denominator will be the ‘at risk’ period i.e. the time to first event. The 95% confidence intervals (CI) will also be reported.

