9.6. Data analysis

Descriptive statistics will be produced for all relevant study measures previously described, for the overall cohort and for each treatment (apixaban and warfarin). Categorical measures will be presented using frequency (number of patients [n]) and percentage (%) of total study patients observed in each category. Continuous and count variables will be presented as the mean, SD, median, minimum, maximum and IQR. As relevant, continuous variables will also be categorized into intervals. Univariate statistics will be calculated for each measure of interest. No comparisons will be made between the two cohorts..

Four multivariable regression models will be developed for this study. Cox proportional hazards models will be conducted to evaluate both the risk (expressed as hazard ratios with corresponding 95% confidence intervals) of discontinuing or switching from the index treatment as well as the risk of experiencing a clinical event (i.e., recurrent VTE, major bleeding, or CRNM bleeding).. The main effect variable will be the treatment cohort (apixaban vs. warfarin, with warfarin as the reference group). Covariates to be considered for inclusion into the models will include demographic and clinical characteristics of interest. A backward elimination of independent variables least associated with the dependent variable may be used. Clinically relevant covariates that are not retained during backward elimination may also be forced into the model. Collinearity among the variables of interest will be evaluated during model development.

Kaplan-Meier analyses will also be utilized to report the time to an event of interest (e.g., switch, discontinuation). Kaplan-Meier is a method for estimating the probability of the proportion of individuals remaining in the sample at a particular time from an initiation point. It takes into account patients lost or censored before the study endpoint. All analyses will be based on observed, not projected, data. Analyses will be conducted using SAS[®] Release 9.4 (SAS Institute Inc., Cary, NC), and the results will be reported in Excel tables.

Any major modifications of primary endpoint definitions (treatment patterns) or their analyses would be reflected in a protocol amendment.

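### Separate Kaplan-Meier curves for switching and discontinuation leave the competing event undefined; if it is censored, as is common, the share who switch is overstated

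*Combined protocol and SAP*

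**What the plan says.** Section 9.2.2 gives each event its own Kaplan-Meier analysis with a median. For discontinuation, "Kaplan-Meier (KM) curves will be generated to measure median time (and 95 % CI) to discontinuation". For switching, "KM curves will be generated to measure median time (and 95 % CI) to switching". Section 9.6 repeats the approach: "Kaplan-Meier analyses will also be utilized to report the time to an event of interest (e.g., switch, discontinuation". On censoring it adds only this: "It takes into account patients lost or censored before the study endpoint". No cumulative incidence function or other competing-risk method is named anywhere. Section 9.6 identifies treatment patterns as the primary endpoint.

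The definitions in section 9.2.2 link the two events:

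- **Discontinuation** is a gap of at least 30 days after run-out of the index drug, "or with no other claims for the respective therapy". Switchers are not exempted. On timing, "The date of the discontinuation will be defined as the last day" covered by the last fill, so the event is back-dated to run-out.
- **Switch** is a fill of another oral anticoagulant, or of a parenteral one, "within 30 days before or after the run out date of index treatment". It is dated at that fill.
- **Persistent days** "will be reported for patients until they discontinue, switch or end of follow-up based on definitions below".

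The number and percentage of patients with each event are also planned.

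**The concern.** The persistence measure treats discontinuation and switch as alternative ends of one treatment episode. A switch counts only near run-out, so a patient who stopped the index drug well before can no longer have one. A Kaplan-Meier curve for switching that censors discontinuers then estimates how many would switch if nobody could discontinue. A descriptive study of treatment patterns needs the share who actually switch.

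The plan does not state the censoring rule, so the reported result depends on a choice left to the analyst. The definitions also overlap. A patient who fills another anticoagulant two weeks after run-out and never returns to the index drug meets both definitions, with discontinuation dated first.

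**Working it through.** The plan gives no switching or discontinuation rate, so there is no figure of its own to reproduce. All rates below are assumptions.

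**Step 1. Switching, with discontinuers censored.** Take constant monthly hazards d for discontinuation and s for switching, one ending per patient, and t = 12 months.

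- One minus Kaplan-Meier: 1 − exp(−s·t)
- Cumulative incidence: s/(s+d) × [1 − exp(−(s+d)·t)]

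| d | s | 1 − KM | Cumulative incidence | Ratio |
|---|---|---|---|---|
| 0.05 | 0.01 | 11.3% | 8.6% | 1.3 |
| 0.15 | 0.01 | 11.3% | 5.3% | 2.1 |
| 0.05 | 0.02 | 21.3% | 16.2% | 1.3 |
| 0.15 | 0.02 | 21.3% | 10.2% | 2.1 |

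For the first row, 1 − exp(−0.12) = 0.113 and (0.01/0.06) × [1 − exp(−0.72)] = 0.086.

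**Step 2. Between cohorts.** Compare the first two rows. Two cohorts with the same switching hazard but different discontinuation hazards have the same Kaplan-Meier switching curve (11.3%), while the shares who switch are 8.6% and 5.3%. The curve hides the difference.

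**Step 3. Median time to switching.** Under these hazards the Kaplan-Meier median is ln 2/s and the share who ever switch is s/(s+d).

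- s = 0.01: the median is 69.3 months, beyond the roughly 60 months from 01 January 2018 to 31 December 2022, so it would be reported as not reached. Ever switching: 0.01/0.06 = 17% or 0.01/0.16 = 6%.
- s = 0.02: the median is 34.7 months, inside follow-up. Ever switching: 0.02/0.07 = 29% or 0.02/0.17 = 12%. The fraction still on the index drug at 34.7 months, even before other censoring, is exp(−0.07 × 34.7) = 8.8% or exp(−0.17 × 34.7) = 0.3%.

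**Step 4. Discontinuation, with switchers censored.** Exchange d and s in the formulas.

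- d = 0.05: 45.1% against 42.8% (s = 0.01) or 40.6% (s = 0.02), ratios 1.05 and 1.11.
- d = 0.15: 83.5% against 80.0% or 76.8%, ratios 1.04 and 1.09.

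A more extreme assumption, with 70% discontinuing and 20% switching by 12 months, gives a ratio of 83.3/70 = 1.19.

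**Step 5. Dependence on the unstated rule.** A simulation of 40,000 patients assumed 12-month incidences of 50% for discontinuation and 5% for switching, with uniform censoring from 30 to 1,800 days.

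| Handling of the other event | Switch, 12 months | Discontinuation, 12 months |
|---|---|---|
| Aalen-Johansen | 5.0% | 50.1% |
| Kaplan-Meier, other event censored | 7.0% | 51.7% |
| Kaplan-Meier, discontinuers kept at risk to end of follow-up | 5.0% | not applicable |
| Kaplan-Meier, switchers counted as discontinuers | not applicable | 55.1% |

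The 55.1% is a valid estimate, but of stopping the index drug for any reason.

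**Step 6. Dates.** Discontinuation is dated at run-out and a switch up to 30 days later. Ordering events by these dates puts discontinuation first for every switch after run-out that also meets the discontinuation definition. Censoring at discontinuation would drop those switches from the Kaplan-Meier curve, and Aalen-Johansen applied to the same dates would code them as discontinuations.

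**The case against.** The strongest reply is that the plan never says the other event is censored. The follow-up rule in section 9.2 lists neither switch nor discontinuation as an end of follow-up, and if discontinuers stay at risk the switching curve is not inflated (step 5). This stands, and it makes the overstatement conditional. It does not remove the gap, because the same data give 7.0% or 5.0% depending on an unwritten choice.

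A second reply is that section 9.2.2 already reports counts and percentages for each event, and persistent days for the composite, and wants the curves only for median times. Those other summaries are indeed free of this censoring problem. But crude percentages mix patients with different lengths of follow-up and so do not give the share at a fixed time, and the median time to switching is the quantity most affected.

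Three stronger readings are tempting, and the documents do not support them:

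- **Both curves are overstated.** Read literally, the discontinuation definition takes in switchers with no further index-drug claims. That curve can then be a valid all-cause stop.
- **The median time to switching is a meaningless extrapolation.** Kaplan-Meier does not extrapolate; an unreached median is reported as such. A reached one is a hypothetical time to switch had nobody discontinued, interpretable under independence but a poor description of actual patients.
- **Cohorts with equal switching hazards would show different Kaplan-Meier curves.** Step 2 shows the reverse.

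**Conclusion.** The concern holds in conditional form. The plan calls for separate single-event curves for two linked primary outcomes and specifies neither a competing-risk method, nor a rule for the other event, nor whether the two are mutually exclusive. If discontinuers are censored, the 12-month share who switch is overstated by a factor of about 1.3 to 2.1 on the hazards assumed here. For discontinuation the factor is about 1.04 to 1.11, and there is no overstatement if switchers count as discontinuers.

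These sizes rest on constant hazards, on rates not taken from the documents, and on one correctly classed ending per patient. If back-dated discontinuation also removes switches after run-out, that pulls the switching curve down, and the documents do not allow the net effect to be worked out. The change should be made before the analysis is run, although the composite persistence measure and the crude counts escape this censoring problem.

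**What to change.** 1. Make the two events mutually exclusive ends of one treatment episode. Class a patient with a qualifying fill within 30 days before or after run-out as a switch, and any other stop as discontinuation, so that back-dating to run-out does not remove later switches.
2. Keep Kaplan-Meier, with its median and 95% CI, for the composite of discontinuation or switch.
3. Report Aalen-Johansen cumulative incidence of switching and of discontinuation at 3, 6 and 12 months with 95% CI, each competing with the other.
4. Drop the Kaplan-Meier median time to switching.

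The cost is a little more analysis work and a short amendment to the outcome definitions; section 9.6 already sends major changes to the primary endpoint definitions or their analyses to a protocol amendment. No new data are needed, and the estimator is a standard option in the planned SAS software (PROC LIFETEST with EVENTCODE). Step 1 cannot be skipped, because Aalen-Johansen on the dates as now defined would understate switching. Section 9.8 says that mortality is not captured, so death cannot be added as a competing event and remains a stated limitation.

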9.1. Study period and study design

The analysis will be conducted using data from 01 July 2017 through 31 December 2022 or the latest available data at the time of extraction (i.e., the *study period*). Figure 1 illustrates the study schematic for this project. The study cohorts will be identified during a selection window from 01 January 2018 to 30 November 2022. The date of the first treatment with apixaban or warfarin during the hospitalization will be flagged. Based on this treatment during the VTE hospitalization, patients will be classified into the apixaban and warfarin cohorts. Patients will be required to have medical and pharmacy activity during the 6 months prior to the admit date of the hospitalization (pre hospitalization period) and 1-month (minimum) from the discharge date of the hospitalization (post hospitalization period). The date of the first outpatient prescription for apixaban or warfarin on or within 30 days after discharge date from the hospitalization will be termed as ‘treatment index date’.

Figure 1. Study Period

*Latest available data at the time of extraction will be utilized for this study

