9.2. Variables

[figure not shown]
From the final sample, the following measures will be reported (Figure 2):

1. Patients with a claim for the respective treatment (apixaban for apixaban cohort or warfarin for warfarin cohort; using NDC from LRx) as their first post-discharge outpatient treatment (on or within 30 days following discharge i.e. discharge date or ≤ 30 days after discharge date) (n, %). These patients will comprise the analytic cohort for outcomes assessment.

- a. The date of the first post-discharge outpatient prescription claim in LRx (apixaban or warfarin) will be defined as the ‘treatment index date’ for patients in both cohorts respectively.
 - b. Patients will be required to have pharmacy stability during the 6-month period preceding the treatment index date, defined as consistent reporting of data in each month from the pharmacy associated with the treatment index date in LRx to ensure continuous visibility within LRx. The number of patients excluded due to lack of stability will be reported (n, %)
 - c. Patients with recurrent VTE, major bleeding, or CRNM bleeding between the discharge date and the treatment index date will be excluded. The number of patients excluded due to these reasons will be reported (n, %).
 - d. Patients will be followed from the treatment index date until the earliest of last prescription, last patient medical claim, end of pharmacy stability, or end of study period using the Dx/Rx databases.
2. Patients with OAC (warfarin, apixaban, rivaroxaban, dabigatran, or edoxaban) other than the respective inpatient treatment as their first outpatient prescription claim (on discharge date or within 30 days of discharge) (NDC codes from LRx; n, %). These patients will be captured as having switched from inpatient therapy and will not be further evaluated for outcomes.
 3. Patients with no post-discharge outpatient prescription claim for any OAC (on or within 30 days of discharge) (NDC from LRx; n, %)

All study outcomes will be evaluated for the apixaban and warfarin cohorts.

Figure 2. Study Flow

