Note: Recurrent VTE will be defined as inpatient hospitalization with a primary diagnosis of VTE occurring 7 or more days after the first hospitalization discharge date.

- Time (days) from first hospitalization discharge date to first recurrent VTE hospitalization (mean, SD, median, IQR, min, max)
- Time (days) from treatment index date to first recurrent VTE hospitalization (mean, SD, median, IQR, min, max)
- Patients with ≥ 1 hospitalization for major bleeding (ICD-10 codes in CDM; n, %)
- IR of major bleeding (per 100 patient years)

Note: Major bleeding will be defined as inpatient hospitalization with primary diagnosis of gastro-intestinal bleeding, intracranial hemorrhage (ICH) or other major bleeding

- Time (days) from first hospitalization discharge date to first major bleeding episode (mean, SD, median, IQR, min, max)
- Time (days) from treatment index date to first major bleeding episode (mean, SD, median, IQR, min, max)
- Patients with ≥ 1 CRNM bleeding event (n, %)
- IR of CRNM bleeding (per 100 patient years)

Note: CRNM bleeding will be defined as inpatient hospitalization with a secondary diagnosis code for bleeding (without a major bleeding code in the primary position) or an outpatient encounter with a diagnosis code in any position for CRNM GI bleeding or other non-critical types of bleeding. Specifically, it is defined as:

(1) An inpatient admission with a secondary diagnosis for “noncritical site” bleeding such as GI bleeding or other selected noncritical types/sites of bleeding (excluded if major bleeding occurred during the same hospitalization), OR

(2) An outpatient encounter with a diagnosis code for GI bleeding and other selected noncritical types/sites of bleeding.

Any CRNM bleeding events (as described above) that follow a major bleeding event (described above) will not be included in the analysis of CRNM bleeding

- Time (days) from first hospitalization discharge date to first CRNM bleeding episode (mean, SD, median, IQR, min, max)
- Time (days) from treatment index date to first CRNM bleeding episode (mean, SD, median, IQR, min, max)

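### Read literally, the incidence-rate denominators for recurrent VTE and CRNM bleeding include days on which the event cannot count, so both rates lean low by an amount the plan leaves open

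*Combined protocol and SAP*

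**What the plan says.** - **Start of outcome time.** Under 9.2.2, outcomes "will be measured during the variable post-index period starting on the treatment index date". Section 9.1 sets that date: the first outpatient prescription "on or within 30 days after discharge date from the hospitalization will be termed as" the treatment index date. The lag from discharge is therefore 0 to 30 days, and 9.2 item 1 confirms that a fill on the discharge date itself qualifies.
- **Numerator.** "The numerator for IR will be the number of patients with the event of interest".
- **Denominator.** The "denominator will be the ‘at risk’ period i.e. the time to first event". Nothing further is said, including how patients without an event contribute.
- **Recurrent VTE.** It counts only as an admission with a "primary diagnosis of VTE occurring 7 or more days after the first hospitalization discharge date".
- **CRNM bleeding.** Events that follow a major bleed "will not be included in the analysis of CRNM bleeding".
- **Limits on time.** Clinical outcomes are assessed only while the patient is persistent on the index drug (9.2.2). Follow-up ends at the earliest of last prescription, last medical claim, end of pharmacy stability or end of study (9.2 item 1d). A major bleed is not in that list.
- **Use in models.** Section 9.6 plans Cox models for these clinical events, with treatment cohort as the main effect. It gives no entry or censoring rule for them.

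**The concern.** A rate is interpretable only if every day in the denominator is a day on which an event could enter the numerator. The plan restricts the numerator in two ways (a 7-day window after discharge for VTE, and no CRNM bleed after a major bleed) without a matching restriction on the denominator. A mismatch of this kind can only lower a rate.

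The VTE part cannot be dismissed in advance, because only persistent time counts and that time may be short. For example, 9.1 allows selection up to 30 November 2022 with data planned to end on 31 December 2022, so late entrants may have about one month of follow-up.

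At stake are the recurrent VTE and CRNM rates reported under the secondary objective, and the composition of the early risk sets in the corresponding Cox models. If the Cox clock starts at the index date, someone who fills on day 0 sits in the risk sets of days 0–6 without being able to have a countable VTE, while someone who fills on day 7 or later can have one.

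**Working it through.** The plan states no rate, event count, fill-timing distribution or persistence, so there is no figure of its own to reproduce. The inputs from the documents are the lag L from discharge to index (0–30 days), the 7-day window, and the rule on CRNM bleeds after a major bleed. All other inputs below are assumed.

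**Recurrent VTE**

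Ineligible days per patient = max(0, 7 − L): 7 for L = 0, 4 for L = 3, 1 for L = 6, and 0 from L = 7. This is a maximum, because persistence may end sooner.

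Relative understatement = mean ineligible days ÷ mean persistent days T.

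Mean ineligible days under three assumed fill patterns:
- All fill on the discharge date: 7.
- 60% on day 0, 5% on each of days 1–6, 10% later: 0.60 × 7 + 0.05 × (6+5+4+3+2+1) = 4.20 + 1.05 = 5.25.
- Uniform over days 0–30: (7+6+5+4+3+2+1) ÷ 31 = 28/31 = 0.90.

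| Assumed mean T (days) | All on day 0 | Mostly early | Uniform 0–30 |
|---|---|---|---|
| 30 | 7/30 = 23.3% | 17.5% | 3.0% |
| 90 | 7/90 = 7.8% | 5.8% | 1.0% |
| 180 | 7/180 = 3.9% | 2.9% | 0.5% |
| 365 | 7/365 = 1.9% | 1.4% | 0.2% |

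In rate terms, suppose the rate over eligible time is 4.00 per 100 patient-years (assumed) and all fill on day 0. The literal denominator gives 4.00 × (T − 7)/T = 3.07, 3.69, 3.84 and 3.92 at the four values of T.

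**CRNM bleeding**

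With a constant major-bleed rate r and persistent time F, and all remaining persistent time kept after the bleed, the share of time after a major bleed is 1 − (1 − e^(−rF))/(rF):
- r = 0.02 per year, F = 0.25 year: 0.25%, or about 0.3%.
- r = 0.04 per year, F = 1 year: 2.0%.

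Numerical integration that also allows for CRNM events (assumed 10–20 per 100 patient-years) gives 0.4%, 0.7% and 1.5% at 90, 180 and 365 days for major bleeding at 3 per 100 patient-years. An extreme case of 10 per 100 patient-years over 365 days gives about 5%. If only a quarter of the remaining time is kept, because most patients stop the drug, that falls to 1.3%.

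**Between cohorts**

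Suppose equal true rates and equal T, with one cohort filling entirely on day 0 and the other uniformly over days 0–30. The ratio of reported VTE rates would be (1 − 7/T) ÷ (1 − 0.90/T) = 0.79, 0.93, 0.97 and 0.98 at T = 30, 90, 180 and 365. This is a deliberate extreme; the documents report no difference in fill timing.

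**The case against.** The strongest defence is that the denominator is called the at-risk period, which in ordinary usage leaves out days when an event cannot count. The explanation that follows may be shorthand: taken strictly, it gives event-free patients no person-time at all. On that view the plan is incomplete rather than wrong, and a careful programmer would do the right thing. Part of this stands: no sentence expressly includes the ineligible days. But the only definition offered points towards inclusion, and no sentence delays entry or censors at the bleed. The two-programmer check in 9.7 does not settle a rule that is not written.

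A reader might infer more than the documents support:
- **That the first 7 days after discharge are in every patient's denominator.** They are not. Time starts at the index date, so only those of days 0–6 on or after the first fill can enter, and patients who fill on day 7 or later add none.
- **That all time after a major bleed is included.** Only time still persistent on the index drug and before the end of follow-up can be.
- **That the VTE rate will be understated by as much as 23%.** That needs everyone to fill on the discharge date and mean persistence of only 30 days.
- **That the apixaban–warfarin comparison is biased.** This would require different fill timing or persistence, which the documents do not report. In the Cox model, risk sets matter only at event times. Events in days 0–6 after index can come only from patients whose lag plus elapsed days has reached 7, so few risk sets are touched.

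It is also fair to say that the bias may be smaller than sampling error. A bias of 3.9% or 1.9% is below one Poisson standard error of the rate unless there are more than about 660 (1/0.039²) or 2,700 (1/0.019²) events. That limits the practical importance, but it is no reason to keep an avoidable error that always points the same way.

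**Conclusion.** The point holds as a mismatch under the literal text of 9.2.2, and its direction is downward for both rates. Its size cannot be fixed from the documents. For recurrent VTE it is at most about 4% if mean persistence is six months or more. It becomes material only if persistence is short and most fills are close to discharge. The CRNM part is minor in nearly every scenario. An effect on the comparison between cohorts is possible but not shown. The primary treatment-pattern outcomes are untouched. Importance is minor to moderate: worth correcting before the analysis because the remedy is standard and cheap.

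**What to change.** In 9.2.2:
1. Start recurrent-VTE time at risk at the later of the treatment index date and day 7 after discharge.
2. End CRNM time at risk at the first major bleed.
3. Define the denominator for all patients, with or without an event, as the sum of time from that start to the earliest of first event, discontinuation, switch or end of follow-up (plus the first major bleed for CRNM).

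In 9.6, state that the Cox models use the same dates, with delayed entry for recurrent VTE.

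The cost is a few sentences and two date variables in the program. The downside is that a few patients whose persistence ends before day 7 after discharge leave the VTE rate; their number should be reported.

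### The raw times to first recurrent VTE, major bleed and CRNM bleed exist only for patients with an event while persistent, so they are confounded with length of persistence; cumulative incidence at fixed times should be specified

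*Combined protocol and SAP*

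**What the plan says.** Section 9.2.2 (Clinical Outcomes) gives the time lines for the three outcomes as plain descriptive statistics. From the treatment index date, the line for recurrent VTE is "Time (days) from treatment index date to first recurrent VTE hospitalization (mean, SD, median, IQR, min, max"; major bleeding and CRNM bleeding each have a line of the same form. Each has a twin that starts at discharge, for example "Time (days) from first hospitalization discharge date to first major bleeding episode (mean, SD, median, IQR, min, max". None of the six carries a censoring rule, a Kaplan-Meier curve or a cumulative incidence.

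The observation window is on-treatment: "The following clinical outcomes will be assessed during the time patients are persistent with their respective index apixaban or warfarin treatment". It also differs between patients. Section 9.2, item 1d, states: "Patients will be followed from the treatment index date until the earliest of last prescription, last patient medical claim, end of pharmacy stability". The close of the study period is the remaining limit.

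The treatment-pattern outcomes in the same section are handled differently. Beside the raw statistics for discontinuation there is a note that Kaplan-Meier "curves will be generated to measure median time (and 95 % CI) to discontinuation", and switching has a matching note.

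The discharge-anchored lines also meet section 9.2, item 1c: "Patients with recurrent VTE, major bleeding, or CRNM bleeding between the discharge date and the treatment index date will be excluded". The treatment index date can fall up to 30 days after discharge.

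**The concern.** The protocol does not say in words that the six summaries are restricted to patients with an event, but it follows: days to a first event cannot be computed for anyone else. Such a time can be observed only if the event comes before discontinuation, switch or end of follow-up. A cohort that stays on drug longer therefore has room for later events, and its typical time to event lengthens even if its hazard is the same.

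The lines will be tabulated for apixaban and warfarin side by side. Section 9.6 says the two cohorts will not be compared, yet it makes treatment cohort the main effect in the Cox models, so readers will compare. A longer time to first bleed in one cohort could be taken as a safety advantage under objective 3 when it reflects only longer persistence.

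The discharge-anchored versions have a further defect. Their clock starts at discharge, but item 1c removes everyone with an event between discharge and the first outpatient fill.

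**Working it through.** The protocol gives no event rate, persistence length or event-time figure, so there is nothing of its own to reproduce. **All rates and durations below are assumptions**: 2 to 20 events per 100 patient-years and median persistence of 90 to 365 days, where persistence includes end of follow-up.

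**1. Constant hazard, variable persistence.** Let the event hazard be λ per day and let persistence be exponential with rate μ = ln 2 / (median persistence), independent of the event. The time among patients whose event is observed then has density proportional to exp(−(λ+μ)t). Its median is ln 2/(λ+μ), and the share of patients with an event is λ/(λ+μ). When λ is small against μ, the median is close to ln 2/μ, which is median persistence.

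At 5 per 100 patient-years, λ = 0.05/365.25 = 0.000137.

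- Median persistence 180 days: μ = 0.003851, so the event-only median is 0.6931/0.003988 = 173.8 days; 3.4% of patients have an event.
- Median persistence 90 days: μ = 0.007702, so the event-only median is 0.6931/0.007838 = 88.4 days; about 1.75% have an event.
- Median persistence 365 days: 340.5 days.

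**2. Sensitivity to the rate.** With median persistence held at 180 days, the event-only median is:

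| Events per 100 patient-years | Event-only median (days) |
|---|---|
| 2 | 177.5 |
| 5 | 173.8 |
| 10 | 168.1 |
| 20 | 157.6 |

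A tenfold change in rate moves the statistic by about 20 days. Halving persistence at 5 per 100 patient-years moves it by about 85 days.

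**3. What a censoring-aware summary shows.** Simulation with 400,000 patients per scenario, both cohorts at the same true rate:

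| True rate per 100 patient-years | Median persistence (days) | Event-only median (days) | Kaplan-Meier incidence at 180 days | Incidence rate per 100 patient-years |
|---|---|---|---|---|
| 5 | 180 | 172.6 | 2.48% | 5.06 |
| 5 | 90 | 87.6 | 2.47% | 5.06 |
| 10 | 180 | 168.4 | 4.84% | 10.07 |
| 10 | 90 | 88.0 | 4.73% | 9.89 |

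At 5 per 100 patient-years the exact 180-day risk is 1 − exp(−0.05 × 180/365.25) = 2.43%. Kaplan-Meier and the incidence rate both show essentially no difference between cohorts; the event-only median shows a twofold one.

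**4. Non-constant hazard.** With a Weibull event hazard set to 5% cumulative incidence at one year, the event-only median in days is:

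| Weibull shape | Median persistence 90 days | 180 days | 365 days |
|---|---|---|---|
| 0.3 | 9 | 18 | 36 |
| 0.5 | 29 | 57 | 114 |
| 0.7 | 52 | 103 | 204 |
| 1.0 | 88 | 174 | 340 |
| 1.5 | 151 | 290 | 537 |

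Reading down a column, the statistic does respond to how front-loaded the hazard is. Reading across a row, it grows roughly in proportion to persistence.

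**5. Discharge-anchored versions.** After item 1c, every remaining discharge-anchored time equals the index-anchored time plus an event-free gap of 0 to 30 days. It adds only the fill delay and cannot describe events soon after discharge. For recurrent VTE, the definition in section 9.2.2 already rules out days 0 to 6; item 1c then also removes later events that precede the fill.

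**The case against.** The strongest reply is that objective 3 does not rest on these six lines. Section 9.2.2 plans incidence rates per 100 patient-years, and section 9.6 plans Cox hazard ratios for the clinical events. Both account for unequal follow-up and would show equal hazards as equal. Persistent days and follow-up duration are reported too, so a careful reader could see the confounder. This stands, and it limits the damage. But neither a rate nor a hazard ratio gives absolute risk by a stated time, and neither corrects the six lines themselves.

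It can also be said that Kaplan-Meier is not ruled out. Section 9.6 plans it for events of interest and names switching and discontinuation only as examples. That is right: for clinical events it is permitted but not committed to.

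A reader might go further and infer that the summaries measure persistence alone and say nothing about how early events occur. That is not supported: step 4 shows a range of 9 to 151 days across hazard shapes at the same persistence. Nor can one say that the typical time is always about half of follow-up. That holds only if all patients share one fixed follow-up length, and the protocol makes follow-up variable. With exponential persistence of median 180 days and 5 events per 100 patient-years, the mean event time is 251 days against a mean persistence of 260.

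Finally, the item 1c effect is bounded: it can remove only times inside a gap of at most 30 days, and the number excluded will be reported. It is a real but limited defect.

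**Conclusion.** The point holds as one of confounding. The six time summaries are conditional on having an event inside a persistence window of variable length. They depend strongly on that length and are nearly insensitive to the event rate when events are rare. With identical hazards of 5 per 100 patient-years and median persistence of 180 versus 90 days, they would show about 174 versus 88 days, against a 180-day incidence of about 2.5% in both cohorts. The size rests on assumed rates and durations, and on persistence being exponential and independent of the event. The direction does not depend on the particular values: in every hazard shape tried, the statistic lengthened with persistence.

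The primary treatment-pattern results are untouched, and the planned rates and hazard ratios for the secondary outcomes remain usable. What needs changing is the reporting of event timing, where the protocol commits to the less informative summary and leaves the better one optional.

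**What to change.** In section 9.2.2, for each of the three clinical outcomes, specify Kaplan-Meier or cumulative incidence from the treatment index date at fixed times (for example 30, 90, 180 and 365 days), with 95% CI and numbers at risk. State the on-treatment censoring rule: discontinuation, switch or end of follow-up, as already defined for persistence. Name the three outcomes in the Kaplan-Meier paragraph of section 9.6.

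If the raw index-anchored times are kept, label them *among patients with an event* and print them beside persistent days for the same cohort.

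Drop the three discharge-anchored lines. Do not repair them by putting the item 1c patients back with the clock at discharge. Objective 3 concerns patients who continue in the outpatient setting while persistent, so that would change its population. It would also create immortal time, because cohort entry still requires a later fill.

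The cost is slightly more analysis output and a few lines of protocol text; no new data are needed.
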